## **10. Risks and Benefits**

### **a. Risks to Subjects**

*Primary Care Practices.* The Practice Survey and the Practice Member Questionnaire descriptively illustrate the participating sites in the study. The surveys are not designed to capture PHI on practices' patient population. For practices, risks associated with participation are minimal as the study seeks to measure quality improvement strategies employed by practice sites through surveys. The survey items are non-intrusive and poses minimal emotional, social, and legal harm to practices. All participating practices will sign a Memorandum of Understanding outlining expectations, responsibilities for participation, and the steps OHSU will take to mitigate risk during the pilot study.

*Patients.* Patient outcomes are integral to interpretation of findings. Chart audits will be conducted such that protected health information (PHI) from patients is not collected and removed from the practice. This complies with federal HIPAA regulations regarding the transferring, storage, and reporting of PHI and ensures patient privacy and confidentiality.

Five patients at each intervention practice (N=20) will be identified and asked to participate in an interview. Using the list of randomly selected patients who meet study criteria and

screen positive for depression, a practice staff member will reach out to patients, using a script that we prepare and is approved by OHSU IRB. This script will guide the staff member to briefly explain the study and ask the patient if they are willing to be contacted (and have their contact information shared) with research staff for further details. Research staff will then contact patients, describe the study and provide more details. If the patient agrees to participate, a member of the research team will schedule an interview. Interviews can be conducted in person at the practice or at a convenient location (e.g., coffee shop, library study room) and / or can be conducted by telephone, if an in-person interview is not possible. Patients will be mailed or emailed an Information Sheet approved by OHSU IRB prior to the interview and the interviewer will bring an Information Sheet to the interview. The interviewer will answer any of the patient's questions about the study, the interview and the Information Sheet, and ask for permission to audio-record the interview. If granted, the interviewer will conduct and record the interview. If not, the interviewer will conduct the interview and take notes, or not conduct the interview at all, if the patient has changed his or her mind about participation. Participants will be instructed that the interview can stop and the recording can end at any time they indicate. The interviewer will ask about the patient's experiences with the INTEGRATE-D intervention at his or her practice and these questions will pose very minimal risk to patients. Interview recordings are professionally transcribed and reviewed for accuracy by the study team. During that process, all information that could be used to identify the patient is removed from the transcript.

Findings from these data, will only be communicated in aggregate and as high-level findings with practices.

**b. Potential Benefits to Subjects**

The minimal risk to subjects is offset by the anticipated benefits of this study. The participants in this study are practices and their members and there are several direct benefits to these participants. Behaviors health clinicians will receive cutting-edge training in the ADA recommendations from the experts who created that curriculum free of cost. Practices will then receive practice support to help make practice improvements. Practice sites will also receive tailored reports and education in how to use them. Practice will also receive expert consultation from leaders in integration. Practices receive this consultation for free. Participation in this study could improve practice capacity and care quality. In addition, the findings from INTEGRATE-D may be used to inform policies and practices regarding how to best implement the ADA recommendations for integrating medical and psychosocial are for patients with DMII, and will be used to inform a scale-up effort among primary care sites, other practices nationwide and the quality improvement organizations that support practice improvement in the US.

### ***The INTEGRATE-D Intervention***

INTEGRATE-D was an implementation support intervention designed to help clinics align care with ADA recommendations. The intervention was initially comprised of 15-months of tailored external support that included three evidence-informed implementation support strategies: (1) Audit and feedback—assisting clinics in accessing actionable data reports to identify care gaps; (2) Skill-building resources—expert training on ADA-recommended care, DD, pragmatic screening and treatment strategies, and education in the medical aspects of type 2 diabetes targeted to BHCs; and (3) Facilitation—monthly, tailored support to help clinics identify and implement changes to align care with ADA recommendations utilizing Plan Do Study Act (PDSA) cycles and the Bodenheimer Building Blocks.

We modified INTEGRATE-D to accommodate strains due to COVID-19 and to align with what we learned from baseline assessments. Table 1 shows clinics received monthly facilitation remotely rather than in person. IC1 received 15 once monthly facilitation meetings; IC2 received 11 due to the delayed intervention start. Facilitation was tailored and included PDSA cycles that tested workflows to incorporate psychosocial screening; facilitators did not use audit and feedback data. We delivered two remote expert trainings to IC1. Trainings were recorded and shared with IC2.

**Table 1. Intervention Components, Description, Frequency and Timeline**

Intervention Component	Who Provided Support	Description	Frequency and timeline
Expert Training	Physician, BHC, and expert in implementing DD	Education for clinical teams in ADA recommendations and self-management support materials  1.Psychosocial care, type 2 diabetes and DD training for all clinical roles delivered by a physician and DD expert 2.BHC training about the role of the BHC in caring for patient with type 2 diabetes delivered by a clinical	IC1 received these remotely March and May 2021  IC2 was given a recording of these trainings. We do not

		psychologist with expertise in integrated behavioral health and primary care	know if these were reviewed by IC2.
Facilitation	Practice Facilitator	
Customized remote once-a-month meetings with an experienced practice facilitator using Bodenheimer's Building Blocks framework utilizing Plan Do Study Act (PDSA) cycles. Meeting topics were tailored to the clinic's experience and aligned with ADA recommendations and included:
 
 
• Patient education materials for BH and self-management support
 
• Implementation of systematic screenings for DD, depression, anxiety
 
• Identifying changes in roles/responsibilities, new processes/workflows for screening and treatment
 
• Identify cross-functional practice team, train team in QI
 
• Proactive outreach to patients regarding DMII, self-management status, community and family needs
 
• Pre-visit planning and huddling, scheduling BHC visits with warm handoffs
 
	IC1: December 2020-February 2022 IC2: June 2021-May 2022

IC=Intervention Clinic; BHC=Behavioral Health Clinician; DD=Diabetes Distress; QI=Quality Improvement; DMII=Type 2 Diabetes Mellitus; ADA=American Diabetes Association

### ***Data Sources and Measures***

Table 2 shows the data sources and measures used to assess the feasibility and effect of INTEGRATE-D.

Table 2. Study measures, variables and data sources

Assess the feasibility, appropriateness and acceptability of INTEGRATE-D		
VARIABLE/ DEFINITION	DATA SOURCE	DATA COLLECTION / ANALYSIS
Acceptability – extent to which intervention is agreeable, palatable, satisfactory	Assessed via survey  and semi-structured interview. Survey had four questions per variable. See Online Appendix for items.	Collected from clinic members exposed to the intervention (intervention clinics) at the end of the intervention.
Appropriateness – extent to which intervention fits and is compatible for addressing issue or problem		Descriptive analysis for ICs only. Survey scores, which ranged from 1 (strongly disagree) to 5 (strongly agree) for each clinic member response were averaged at the clinic-level.
Feasibility – extent to which an intervention can be successfully used or carried out		
Compare changes in use of quality-improving strategies		
Clinics' ability to implement quality improving strategies related integrated type 2 diabetes care	Assessed via survey using 14 items from the Change Process Capability Questionnaire (CPCQ).  See Online Appendix for items.	One person at intervention and control clinics completed the survey at the same time, pre- and post-intervention.  Survey scores, which ranged from -2 (strongly disagree) to +2 (strongly agree), were summed for each clinic with possible sums ranging from -28 to +28. Average aggregate scores were compared between intervention vs. control clinics
Compare changes in process of care screening rates		
A1C screening – binary variable indicating whether the patient was screened at least once during the period	Electronic Health Record (EHR) data abstracted through manual and automated methods	Operationalized at the patient level for pre- and post-intervention periods, means aggregated at the clinic-level for intervention and control clinics. Pre-intervention defined as the time during the 12 months before the intervention; post-intervention defined as any time during the 12 months following the start of the intervention.
Cholesterol screening - binary variable indicating whether the patient was screened at least once during the period		
Nephropathy screening - binary variable indicating whether the patient was screened at least once during the period		
Psychosocial screenings – binary variables indicating whether the patient was screened at least once during the period for depression (PHQ-2 and/or PHQ-9) and / or for diabetes distress (DD) 		
Compare changes in clinical outcomes (PHQ-9 scores and A1C levels)		
Behavioral health – change in symptoms (PHQ-9) for patients with depression symptoms (PHQ-9>9); data abstracted through manual and automated methods	Operationalized at the patient level for pre- and post-intervention periods, means aggregated for intervention and control clinics; pre-intervention defined as score closest to the intervention start date; post-intervention defined as score closest to the intervention end date.	
Diabetes Management – change in A1C for patients diagnosed with type 2 diabetes		
Confounding Variables - Patient socio-demographics, comorbidity, insurance, and utilization		
Age, gender, language preference, race/ethnicity, income/federal poverty level, insurance type, physical, mental/behavioral health comorbidity, healthcare utilization	EHR data abstracted through manual and automated methods	Operationalized at the patient level

 Diabetes distress (DD) screening was implemented by intervention clinics; clinics did not screen for this pre-intervention

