## ***Data Collection***

We evaluated quantitative data 12 months before the first facilitation visit (pre-intervention) to six-months after the last facilitation visit (post-intervention). Pre-intervention interviews and survey data were collected between November 2020 and July 2021. We delayed the intervention start for Intervention Clinic 2 (IC2) to allow them to prioritize their COVID response, adjusting data collection for IC2 and its matched control clinic 2 (CC2). Monthly check-in calls with ICs started in the month following the first intervention visit (December and June, respectively) and continued for the duration of the intervention. Post-intervention survey and interviews were conducted between March and June 2022 for IC1 and between June and July 2022 for IC2.

Survey data. We conducted two surveys. One was completed by the office manager or clinical leader from each clinic (N=4). This survey collected clinic demographic data and 14 items from the Change Process Capability Questionnaire (CPCQ), which was modified to assess a medical groups use of quality improvement strategies aligned with improve type 2 diabetes care.

Demographic data were collected once, pre-intervention. The CPCQ was completed pre- and post-intervention (see Appendix 2). ICs and CCs completed this survey with a 100% response rate. The second survey assessed the feasibility, acceptability and appropriateness of INTEGRATE-D using three psychometrically assessed measures developed by Weiner et al. This survey was distributed to clinical team members exposed to the intervention (N=17) after the intervention ended, with an 82% response rate. Surveys were conducted using REDCap.

EHR data. EHR data were abstracted through a combination of manual and automated reporting, both of which followed a protocol. Research staff assisted clinic staff with creating a list of patients with type 2 diabetes seen in the clinic at least once in the 15 months prior to the

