### ***Analysis***

Feasibility, acceptability and appropriateness of INTEGRATE-D were assessed post-intervention among ICs. For the other quantitative variables, we compared differences in values pre- and post-intervention among ICs and CCs. For the CPCQ as well as for feasibility, acceptability and appropriateness, we performed clinic-level analyses. For process-of-care measures, we performed patient-level analyses, with results summarized by clinic. When testing the effect of INTEGRATE-D on these outcomes, the independent variables were exposure to the intervention (whether the patient was associated with a clinic randomized to the intervention) and time period where baseline represented the closest measure available for the patient before the start of the intervention and follow-up represented the closest measure after the end of intervention.

To assess the effect of the intervention on A1C and PHQ-9 outcomes, we compared ICs and CCs performing a patient-level analysis using linear mixed effects models. We modeled the outcome of interest as a function of the indicator for period (post vs. pre), indicator for intervention arm (IC vs. CC), and the interaction between period and intervention, using random effects to account for repeated measures within the same patient over time. We adjusted for potential confounding using a range of patient-level characteristics (see Table 2). Statistical tests were two-side ( $\alpha=0.05$ ) and performed in R (version 4.2.0).

Qualitative researchers with expertise in primary care, integrated care and implementation science conducted analyses. We used a group process to analyze qualitative data, tagging text to assign codes that were aligned with emerging patterns/findings. When codes were clearly defined (i.e., we had a codebook) and used consistently among the team, we transitioned to individual data analysis. The team continued to meet to review work and discuss emerging findings. Tagged data was analyzed a second time to examine the similarities and differences across the two ICs. Qualitative findings were summarized and connected with quantitative findings to explain the study results.

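### Follow-up PHQ-9 depends on who is re-screened in routine care, which the intervention can change; the PHQ-9 comparison could be biased either way, and no check is planned.

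*SAP*

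**What the plan says.** **Source.** SAP, Data Collection: "EHR data were abstracted through a combination of manual and automated reporting". No study-administered PHQ-9 is described.

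**Follow-up value.** SAP Table 2 gives it as "defined as score closest to the intervention end date", which allows a score from before that date. The SAP Analysis section says that "follow-up represented the closest measure after the end of intervention", which does not. That sentence stands in a paragraph that opens with process-of-care measures, so whether it also governs PHQ-9 is unclear. Data Collection sets the outer limits: 12 months before the first facilitation visit to six months after the last.

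**Who is included.** Sampled patients needed a visit in the 15 months before the start and another during the intervention. A follow-up PHQ-9 was not required. Table 2 confines the PHQ-9 outcome to patients with a score above 9. Under Hypothesis 4, the protocol estimates change in patients who appear in both periods.

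**What the intervention does.** SAP Table 1 lists "Implementation of systematic screenings for DD, depression, anxiety" among the facilitation topics, and the intervention section says that facilitation "included PDSA cycles that tested workflows to incorporate psychosocial screening". Screening is also an outcome in its own right: Table 2 has "binary variables indicating whether the patient was screened at least once during the period for depression" and for diabetes distress.

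**Model.** A linear mixed model with period, arm and their interaction, "using random effects to account for repeated measures within the same patient over time", adjusted for the Table 2 patient characteristics. Neither document describes the handling of missing follow-up scores or a sensitivity analysis for them. The protocol's diagnostics under Hypothesis 4 concern influential points and model form.

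**The concern.** The intervention acts on the process that produces the outcome data. If it succeeds, intervention clinics will score more of their patients routinely, including those who have recovered. Control clinics may score a more selected group. The mixed model handles missing follow-up correctly only if, given baseline score and covariates, being re-scored is unrelated to the score that would have been found. Current symptoms are a plausible reason for giving a PHQ-9 outside systematic screening, so the assumption is open to doubt, and more so in one arm than in the other.

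At stake is hypothesis 4 for PHQ-9. An arm difference could arise, or be hidden, because different kinds of patients were measured, and that estimate could then be carried into planning of the larger trial.

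**Working it through.** **Sample.** The protocol's total reproduces: 4 practices × 80 = 320. The SAP's two patient lists sum to the protocol's 80 per practice (50 + 30 = 80), so I read both as per clinic. At most 2 × 30 = 60 patients per arm supply PHQ-9 outcomes. The documents give no PHQ-9 standard deviation, effect size or re-screening rate. All inputs below are assumptions, with a true effect of zero. Negative values favour the intervention.

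**General formula.** Let f be the share without a follow-up score, and d the mean unseen score minus the mean observed score. The observed mean differs from the full mean by −f·d, so

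apparent difference (intervention − control) = f_C·d_C − f_I·d_I.

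With f_I = 0.2 and f_C = 0.5:

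- d_C = −3, d_I = 0: 0.5 × (−3) = −1.5
- d_C = +3, d_I = 0: +1.5
- d = −3 in both arms: −1.5 + 0.6 = −0.9
- d = +3 in both arms: +0.9
- d = 0 in both arms: 0, whatever the follow-up rates

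So different rates alone cause no bias. The sign depends on who is missed.

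**What the mixed model removes.** Assume PHQ-9 has mean 9, SD 6 and pre-post correlation 0.5, keep baseline above 9, and let 90% of intervention patients be re-scored regardless of score.

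- Share still above 9 at follow-up: 1/2 + arcsin(0.5)/π = 2/3.
- Their mean follow-up: 9 + 6 × [0.3989 × 1.5 × 0.5 ÷ (1/3)] = 14.386. For the others it is 5.410. Overall: 2/3 × 14.386 + 1/3 × 5.410 = 11.394.
- Mean baseline of the same two groups: 14.386 and 12.590; overall 13.787.
- Within-patient correlation as a random-intercept model sees it: covariance 6.54 ÷ average variance (13.08 + 30.27)/2 = 0.30.
- Model estimate of the follow-up mean: mean of those re-scored − 0.30 × (their baseline mean − 13.787).

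Example: controls are re-scored with probability 70% if still above 9 and 60% if not. The share re-scored is 0.7 × 2/3 + 0.6 × 1/3 = 0.667. Their follow-up mean is (0.4667 × 14.386 + 0.2 × 5.410)/0.6667 = 11.693, and their baseline mean is 13.847. The model gives 11.693 − 0.30 × 0.060 = 11.675, which is 0.28 too high. The apparent effect is −0.28.

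| Control re-scored if >9 / if not | Share re-scored | Follow-up mean, those re-scored only | Mixed model |
|---|---|---|---|
| 70% / 60% | 67% | −0.30 | −0.3 |
| 80% / 40% | 67% | −1.20 | −1.1 |
| 60% / 60% | 60% | 0 | 0 |
| 60% / 70% | 63% | +0.31 | +0.3 |
| 40% / 80% | 53% | +1.50 | +1.4 |

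Simulations under this set-up gave −0.29 to −1.14 when symptomatic controls were favoured and +0.35 to +1.36 with the rates reversed.

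**A second set of assumptions.** Baseline is normal (14, SD 4) cut off at 9. Follow-up is 11 + 0.5 × (baseline − 14) plus error of SD 4.5. Where re-screening is selective, its odds double (or halve) per SD of follow-up score. Likelihood-based estimates of the null effect, with re-screening of 80% (intervention) and 50% (control) unless stated:

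- Random in both arms: 0.0
- Control favours sicker patients: −1.3. Control favours improved patients: +1.3
- Same selection in both arms: −0.8 (sicker) or +0.8 (improved)
- Intervention favours sicker patients, control random: +0.5
- Control selects on baseline score only: 0.0 (a completers' change score would show +0.5)
- Control favours sicker patients, 70% versus 60%: −1.1; 90% versus 30%: −1.9

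**Scale.** With an assumed SD of change of 5, and 0.8 × 60 = 48 versus 0.5 × 60 = 30 patients observed, SE = 5 × √(1/48 + 1/30) = 1.16 points before any allowance for clustering. The bias can be about as large as the standard error.

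**The case against.** A reader might infer that the comparison is biased toward the intervention. The documents do not support that: nothing in them says which patients control clinics re-scored, and reversing the assumed control rates reverses the sign. A reader might also infer that any chart value could serve. In fact Data Collection sets an outer window, and the Analysis section, if it governs PHQ-9, requires a score after the end of the intervention.

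Other points stand in part:

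- The model adjusts for healthcare utilization and behavioral health comorbidity, both plausible drivers of re-screening. Neither calculation includes covariates, so both may overstate the bias. This protection does not reach selection on current symptoms beyond those variables.
- The contrast in screening may be modest. Facilitators did not use audit and feedback data; the second intervention clinic had 11 sessions rather than 15 and received the trainings as recordings that may not have been viewed. That argues for reporting the actual follow-up rates.
- The protocol's Study Design section already calls the evidence preliminary, and hypothesis 4 is secondary and framed as a trend. This limits the seriousness of the point. It does not tell a reader whether the PHQ-9 estimate reflects symptoms or measurement.

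**Conclusion.** The gap is real, and its effect is conditional. Follow-up PHQ-9 is an unscheduled chart score, the intervention can change who has one, and the plan neither describes nor tests the resulting missingness. Bias requires that re-screening depend on the unseen score after allowing for baseline and covariates. If so, a null effect shifts by roughly 0.3 to 1.3 points in either direction across most of the assumed settings (1.4 in the largest reversed case and 1.9 at 90% versus 30% follow-up), and by about zero if control re-screening is random or depends only on baseline. Bias toward the intervention is plausible but not established. Every rate is an assumption, so these figures show what is possible and do not estimate what happened. For a secondary outcome in a four-practice pilot, this is something that should be addressed; it does not invalidate the study.

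**What to change.** 1. Reconcile SAP Table 2 with the Analysis section: state whether a PHQ-9 from before the end of the intervention can count as follow-up. This decides who is missing.
2. Report by clinic the number and share of patients with baseline PHQ-9 above 9 who have a follow-up score, its timing relative to the end date, and the baseline scores of those with and without one. This table shows the problem but does not remove it.
3. Add a delta (tipping-point) analysis. Shift the model-predicted unseen scores by, say, 1, 2 and 3 points both better and worse, in each arm separately. Shifting only control scores, and only for the better, would build in the answer. Each shift moves that arm's mean by the shift times its share missing; for example, 3 points with 50% missing moves it 1.5.
4. If the hypothesis 4 PHQ-9 result changes under plausible shifts, say that it cannot be separated from a change in who was measured.

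This is a cheap improvement: one clarified definition, one table and one sensitivity analysis on data already abstracted. The downside is some extra analysis and possibly a weaker PHQ-9 headline.
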